Scoliosis is broadly defined as deviation of the normal vertical alignment of the spinal column. Scoliosis is typically classified as congenital, neuromuscular, syndromic, or idiopathic and may be treated with observation, bracing, or surgical correction, depending on the severity and the clinical status of the patient.[1] Idiopathic scoliosis represents the most common pediatric subtype and has a prevalence of 0.5 – 5.2%, with an operative rate ranging from 3.9 – 9.8 operations per 100,000 members of the general population.[2-4] Post-operative pain following the surgical correction of pediatric scoliosis is inevitable and must be well managed to achieve the goals of patient comfort, early mobilization, and early discharge. As a result of the short- and long-term adverse effects of opioid use in the pediatric population, many practices are adopting multimodal pain management strategies to reduce the reliance on opioid analgesia.[5, 6]

Virtual reality (VR) has been extensively studied in regards to its ability to reduce peri-procedural pain and anxiety in a pediatric population.⁷ Non-pharmacological methods of distraction are a well-established method of pain control. Virtual reality, by providing a more interactive and immersive experience, has the potential to out-perform other distraction techniques. However, the specific impact of VR following scoliosis surgery has yet to be assessed.⁸ At Connecticut Children's, patients undergo multimodal pain management following scoliosis correction, including narcotics, muscle relaxants, anti-inflammatories, and gabapentin. Patients are also expected to participate with physical therapy daily. In the present study, we intend to investigate the effect of VR on subjective post-operative pain, total inpatient narcotic administration, and mobilization with physical therapy.

Research Question

Does implementation of VR reduce pain, reduce total narcotic administration, and increase mobilization with physical therapy in the immediate post-operative period following spinal deformity surgery in the pediatric population?

Primary and Secondary Aims

Primary Aim(s):

- To determine if virtual reality (VR) reduces the subjective perception of pain for pediatric patients in the acute post-operative period (until discharge) following spinal deformity surgery.
 - Hypothesis: The mean self-reported pain level using a 10-point numeric pain scale will be a minimum of 1 point lower in patients receiving VR compared to those in the control group.

Secondary Aims:

- To determine if VR reduces the total amount of inpatient narcotic use in the acute post-operative period (until discharge) following spinal deformity surgery.
 - Hypothesis: Patients receiving VR will have reduced total inpatient narcotic administration during their hospital stay compared to those in the control group.
- To determine if VR can facilitate earlier mobilization following spinal deformity surgery.

- Hypothesis: Patients receiving VR will participate in a fewer number of physical therapy (PT) sessions prior to receiving clearance for discharge by PT staff.

Outcome Definitions/Data Points Collected

Primary Outcome:

Pain will be measured through the 10-point numeric pain scale self-reported by the patient (patient's will be between 13-18 years of age).

Secondary Outcomes:

- Mobilization will be assessed by the number of PT sessions prior to receiving clearance for discharge by PT staff.
- Patient post-operative gross motor activity level will be measured via wearable Fitbit
- Opioid utilization will be assessed by calculating the total inpatient dose of opioids administered (as documented in the EMR) during the post-operative period.
- Side effects from virtual therapy, including headaches, vertigo, and nausea

Data collected:

- Patient demographics
 - Age, Sex, Race, Language, Ethnicity
- Patient Past Medical History
- Patient medication/drug history (prescription and recreational)
- Prior experience with VR
- Surgical details
 - # of spinal levels involved in fusion
 - Duration of surgery
 - Surgical blood loss
 - Need for transfusion
 - Complications
- Radiographic imaging
- 10-point numeric pain scale ratingsPhysical Therapy notes
 - Number of sessions prior to discharge clearance, timing of sessions, duration of each session, comments from each session,
- EPIC Medication History
- Length of stay
- Timing and duration of virtual reality sessions
- Side effects from virtual therapy sessions
 - Seizures
 - Loss of awareness
 - Headaches
 - Vertigo
 - Nausea
 - Eye strain / blurred or double vision
 - Eye or muscle twitching

- Involuntary movements
- Dizziness and lightheadedness
- Disorientation
- Impaired balance and hand-eye coordination
- Excessive sweating
- Increased salivation
- Drowsiness
- Fatigue
- Motion sickness
- Skin irritation
- Low temperature burns
- Hair loss
-

Study Design

Mixed methods with a prospective cohort and retrospective chart review.

Target Population

Pediatric patients (ages 13-18) undergoing corrective scoliosis surgery at Connecticut Children's over a span of 12 months (03/01/24-03/01/25).

Inclusion/Exclusion Criteria

Inclusion:

Prospective:

- All pediatric patients (ages 13-18) at Connecticut Children's undergoing surgical correction for idiopathic scoliosis over a span of 12 months (03/01/24-03/01/25) will be eligible for inclusion in the prospective arm.

Retrospective:

- All pediatric patients (ages 13-18) at Connecticut Children's that underwent surgical correction for idiopathic scoliosis in the retrospective time frame (03/01/19 - 03/01/24) will be eligible for inclusion in the retrospective arm.

Exclusion:

- History of seizures
- Cognitive developmental delay precluding participation in VR
- Head or neck surgery that does not allow a head-mounted display to be worn safely
- Chronic pain requiring the daily use of opioids for more than 2 weeks prior to the procedure
- Non-English speakers
- Side effects during screening
- Patients with vagal nerve stimulators, cardiac pacemakers, and/or cochlear implants that may receive interference from the VR device

Sampling Method/Recruitment Process

Prospective cohort sample:

All pediatric patients (ages 13-18) undergoing corrective scoliosis surgery at Connecticut Children's over a span of 12 months (03/01/24-03/01/25) will be approached by a study team member during the pre-operative stage with information and consent documentation about the study. If the patient acknowledges that they are interested and would like more information, then the study team member will complete the formal consent and HIPAA process with the patient and family. This will take place in a private setting, and the patient/family will be given ample time to read the consent and have any questions answered. As a part of the consent and HIPAA, patients will consent to the study procedures as well as the research study team accessing their medical record for data collection. Each patient's MRN will be entered into a secure password protected Excel enrollment log and be given a subject identification number for de-identification. During the consenting procedure, the patient will utilize the VR device for 5 minutes to screen for side effects and become accommodated to the device. In the event that the patient experiences side effects during this 5-minute period, they will be excluded from the study.

Retrospective chart review sample:

The retrospective chart review is intended to be used as a historical control to the prospective arm of the study. All patients in the retrospective time frame (02/01/19 - 02/01/24) will be identified using CPT codes (fusion codes: 22800, 22802, 22804 and instrumentation codes: 22842, 22843, 22844) as well as ICD-10 Code M41.* from Slicer Dicer. These patient's charts will be verified by a study team member to ensure they meet inclusion criteria, and then they will be entered into a using a secure password protected Excel enrollment log. Each patient's MRN will be recorded into the enrollment log and will be given a subject identification number for de-identification. Patients in this cohort will not be approached for consent as we will not collect identifiable information and only their deidentified medical record will be in review. It is also likely that some patients are no longer clinically active at Connecticut Children's, and therefore we would not be able to contact these patients for consent.

Study Retention/Withdrawal

Prospective Cohort:

All patients will be admitted after surgery. It is anticipated that some subjects may opt to not continue with VR and withdraw from the study. Participants will be told that they may withdraw from the study at any time by reaching out to the PI, [name], or the study coordinator, [name]. Withdrawing from the study will not affect patient care. A patient may also decline participation for a VR session, but choose not to withdraw from the entire study. If a patient declines three consecutive VR sessions, then they will be withdrawn from the study. If a patient withdraws, any data already collected will be made de-identifiable and no further information will be collected. These patients will not be included in downstream analyses.

Retrospective Cohort:

These patients will not be approached for consent and therefore will not be able to withdraw from the study.

Study Procedures

Due to the limited number of corrective surgeries for scoliosis in a given year, a true randomized control trial cannot be performed. As such, a prospective cohort will be used – all patients undergoing surgery during the study period will be offered VR and will be assessed for pain, opioid usage, and mobilization following surgery. These outcome measures will be compared to data identified from a retrospective chart review of children receiving the same surgery but without an additional VR-intervention, thus serving as a historical control.

Prospective Arm:

After consenting to the study, the following baseline assessments will be performed and collected from the patient during the pre-operative stage: pain level and vital signs (heart rate, blood pressure, O2 saturation). Starting on postoperative day 1, the prospective cohort will begin receiving VR. These sessions will occur twice daily, starting 30 minutes prior to the patient's scheduled PT appointments, and will be facilitated by a study team member. At the beginning of the session, a study team member will visit the patient's room and set up the virtual reality device. A study team member will try to stay with the patient for the duration of the VR session, but in the event that they are unavailable to do so, a member of the nursing team, physical therapy team, or a parent will remain with the participant. As such, there will always be an adult in close proximity to the participant while they use the VR device. The duration of the session will last approximately 20 minutes and will utilize a low physical load VR experience (underwater or space exploration). The goal of the VR experience is to immerse the patient in a setting that gives the experience of decreased weight bearing load to decrease their post-operative pain. The VR screen will display a simulated environment, such as an underwater exploration, in which the participant can interact with floating marine life and vegetation. If the patient experiences side effects or would like a break during the VR intervention, they can inform a study team member and remove the VR device. They are permitted to place the VR device back on and continue the session when they feel comfortable to do so. A session will be considered "failed" if more than 50% of the session is spent not using the VR device. During the post-operative stage, the above outcome measures will be reassessed daily immediately before and after VR and also following the PT session. After the patient is discharged, the total number of PT sessions and total administered opioids will be collected from the patient's medical charts. In addition to pain, opioid usage, and mobility data from the study, the following information will be collected from the patient charts and entered into REDCap: demographics, degree of scoliosis, surgical details, PT notes, pain medication regimens, associated pain scales, and relevant follow up notes. As the VR device will be shared between users, the device will be sanitized with UV LEDs by Cleanbox prior to the transfer between patients.

Retrospective Arm:

Eligible patients verified for the retrospective chart review will be entered into a secure Excel enrollment log and be deidentified by using a subject identification number. The MRN and subject ID will be entered into a linking file that will be password protected and only accessible to authorized study personnel. The following information will be collected from the patient charts: demographics, degree of scoliosis, surgical details, PT notes, pain medication regimens, associated pain scales, and relevant follow up notes. These data will be entered into REDCap in a de-identified manner and will only be accessible to authorized study team members.

Sample Size Justification

This study will utilize a convenience sample of patients presenting to Connecticut Children's for a scoliosis surgery within the study timeframe.

Feasibility, Accrual, and Duration of Accrual

Accrual will occur over a 12 month period (03/01/24 - 03/01/25). Approximately 60-80 patients undergo a surgical procedure for the correction of scoliosis annually at Connecticut Children's. We estimate ~40% will decline to participate, therefore we anticipate approximately 35-50 patients being included in the prospective arm of study. For the retrospective arm of the study, we approximate to include 350 patients for chart review.

Study Limitations

This study is limited in that we are only assessing the utility of VR to reduce pain in a specific patient population (pediatric patients undergoing surgical correction of scoliosis), at a specific time (the immediate post-operative period), at a single institution (Connecticut Children's), and within a relatively small sample size, which limits the generalizability of the study to apply to other patient populations. This study is also limited in that it utilizes a retrospective chart review as a historical control. By collecting data retrospectively, it is likely that the study team will encounter missing variables and will not be able to categorize pain as accurately as they would be able to in a prospective or true randomized control trial study designs.

Data Analysis

- Intention to treat analysis
- A biostatistician will assist in analysis
- Descriptive statistics (frequency, percentage, mean, standard deviation, median, and interquartile range) will be utilized to describe the two groups (VR and control)
- Fisher's Exact test, independent t-tests, and Wilcoxon Rank Sum tests will be used for univariate analysis to compare demographics between the two groups (VR and control)
- Pain outcome:
 - Univariate analysis using independent t-tests or Wilcoxon rank sum tests will be used to compare the daily mean pain scales
- Opioid utilization outcome
 - Univariate analysis using independent t-tests or Wilcoxon rank sum tests will be used to compare the total inpatient dose of opioids administered

Administrative Organization/Roles and Responsibilities

- Principal Investigator - [name] - Connecticut Children's Division of Neurosurgery
- Co-Principal Investigator – [name] – UConn Department of Psychological Sciences
- Co-Principal Investigator – [name] – Connecticut Children's Division of Orthopedic Surgery
- Co-Principal Investigator – [name] MPH – Connecticut Children's Division of Pain and Palliative Medicine
- Student Coordinators and Responsibilities:
 - [name] – Study Coordinator
 - Study Design

- Data quality
- Data analysis
- Project management
- Manuscript drafting
- [name] – Medical student
 - Study design
 - Study Procedures
 - Data analysis
 - Manuscript drafting
- [name] – Medical Student
 - Study Design
 - Study procedures
 - Data analysis
 - Manuscript drafting

Use of Study Results

The data generated from this study will be used to re-evaluate the postoperative pain management pathway for pediatric patients in the post-operative period following spinal deformity surgery. These data will also be used for presentations / publications.

Study Budget

Item	Quantity	Per
VR Computer	1	\$3,100
VIVE Wireless Head Mounted Display	1	\$1,100
Cleanbox	1	\$2,000
Computer supplies (external hard drives, batteries, sanitizer wipes)	1	\$200
VR Software	1	\$500
TOTAL		\$6,900

References:

1. Janicki, J.A. and B. Alman, *Scoliosis: Review of diagnosis and treatment*. Paediatr Child Health, 2007. **12**(9): p. 771-6.

2. Al-Mohrej, O.A., S.S. Aldakhil, M.A. Al-Rabiah, and A.M. Al-Rabiah, *Surgical treatment of adolescent idiopathic scoliosis: Complications*. Ann Med Surg (Lond), 2020. **52**: p. 19-23.
3. Sung, S., et al., *Incidence and Surgery Rate of Idiopathic Scoliosis: A Nationwide Database Study*. Int J Environ Res Public Health, 2021. **18**(15).

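### The opioid total has no defined start and runs to discharge, so differences between eras in day-0 dosing or length of stay can shift it without any VR effect

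*Combined protocol and SAP*

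**What the plan says.** - **Aim and hypothesis** (Primary and Secondary Aims). The aim is "To determine if VR reduces the total amount of inpatient narcotic use in the acute post-operative period (until discharge) following spinal deformity surgery". The hypothesis is "Patients receiving VR will have reduced total inpatient narcotic administration during their hospital stay compared to those in the control group".
- **Outcome** (Outcome Definitions, Secondary Outcomes). "Opioid utilization will be assessed by calculating the total inpatient dose of opioids administered (as documented in the EMR) during the post-operative period". No clock time or event marks the start of this period, and the dose is not expressed per day or over a fixed window.
- **Intervention** (Study Procedures, Prospective Arm). "Starting on postoperative day 1, the prospective cohort will begin receiving VR". Sessions are twice daily, each starting half an hour before physical therapy (PT).
- **Capture** (same section). "After the patient is discharged, the total number of PT sessions and total administered opioids will be collected from the patient's medical charts".
- **Analysis** (Data Analysis). "Univariate analysis using independent t-tests or Wilcoxon rank sum tests will be used to compare the total inpatient dose of opioids administered". No covariate is named.
- **Stay** (Outcome Definitions, Data collected). "Length of stay" is listed as a data item but does not enter the opioid comparison.
- **Controls** (Inclusion/Exclusion Criteria; Sampling Method; Study Procedures). The controls are a non-randomised historical group from 2019 to 2024. The VR cohort runs from March 2024 to March 2025.

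Study Limitations mentions the historical control, missing variables and less accurate pain data. It does not mention the opioid window.

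**The concern.** A whole-stay total has three parts: the dose before VR can act, the daily dose afterwards, and the number of days over which that daily dose is summed. Post-operative VR sessions can change only the second and third parts. Changes in practice between the two periods can move all three.

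Randomisation would balance the first part in expectation, and would let a difference in stay be attributed to treatment. Neither holds with controls drawn from up to five years earlier. The protocol's background says that many practices are moving to multimodal regimens to rely less on opioids, and it names early discharge as a goal. Drift in both directions is therefore plausible, although nothing shows that it happened at this hospital.

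The results are meant to inform the hospital's post-operative pain pathway. A lower total caused by earlier discharge or changed day-0 practice could be read there as opioid sparing by VR.

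**Working it through.** **The plan's own figure.** The documents give no power, effect size, dose or stay figure for the opioid outcome. The only related number is accrual (Feasibility section): 60-80 operations a year with about 40% declining. 60 × 0.60 = 36 and 80 × 0.60 = 48, which agrees with the stated 35-50. About 350 retrospective charts are expected.

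**Assumptions for illustration.** Day 0 is a share p = 20-40% of the control total, and the rest is spread evenly over 4 further days.

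1. *Stay half a day shorter, daily dose unchanged.* Fall in total = 0.5 × (1 − p)/4. For p = 0.2 this is 10%, and for p = 0.4 it is 7.5%. A full day shorter doubles these to 20% and 15%.
2. *Day-0 dose 20% lower in the VR era, no other change.* Fall in total = 0.20 × p, which is 4% to 8%.
3. *What day-0 doses do to a real effect.* Take a control total of 100 with p = 0.3 and a true 20% cut after day 0. Dose after day 0: 70 against 56, a difference of 14. Total: 100 against 86, again a difference of 14. The mean difference that a t-test examines is unchanged, and only the percentage shrinks (20% to 14%).
4. *Noise.* Assume a day-0 mean of 40 units (gamma, shape 7), a daily dose with mean 30 and SD 10, and days after day 0 with mean 4 and SD 1, all independent. Variance after day 0 is 30² × 1² + 4² × 10² + 10² × 1² = 2,600, so the SD is 51. Day-0 variance is 40²/7 = 229. The SD of the total is √2,829 = 53, about 4% larger.

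**How often the planned test would be positive with no VR effect.** This simulation used the assumptions of step 4, with stay rounded to whole days, 35 or 50 VR patients against 350 controls, a two-sided 0.05 level (the plan states none) and 1,500 runs per scenario. Ranges cover the Welch t-test, the Wilcoxon test and both sample sizes.

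| Difference between eras | p < 0.05 on the whole-stay total |
|---|---|
| None | 5-6% |
| Stay 0.5 day shorter | 36-50% |
| Stay 1 day shorter | 93-97% |
| Day-0 dose 20% lower | 15-17% |
| Day-0 dose 40% lower | 40-55% |
| Stay 0.5 day shorter and day-0 dose 20% lower | 71-84% |

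A two-day window from day 1, tested by Welch t-test, stayed at 4.1-5.6% throughout. This is largely by construction: the simulation let only stay and day-0 dose differ, and it counted two full days for every patient. It shows that the window removes these two sources and no others.

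**Check on a per-day rate.** Suppose stay falls from 4 to 3.5 days and the lost half-day was dosed at half the average rate. The total falls to 1 − 0.5 × (0.5/4) = 0.9375 of its former value, and stay falls to 3.5/4 = 0.875. Dose per inpatient day becomes 0.9375/0.875 = 1.071, a rise of 7.1% with no change in treatment effect.

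**The case against.** The strongest reply is that the whole-stay total is what the sponsor asked about. The aim runs to discharge and the hypothesis covers the hospital stay. Another hypothesis is that VR patients need fewer PT sessions before clearance, so a shorter stay may be one way in which VR lowers opioid use. Removing stay from the outcome, or adjusting for it, would discard part of a possible effect. This stands, and it is why the total should remain the declared outcome.

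Four stronger readings are tempting, and the documents do not support them:

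- *The plan expressly counts day-0 doses.* It does not say so. Inclusion is the plain reading of a post-operative inpatient total, but the documented gap is an undefined start.
- *A real 20% effect would be cut to 16-12%.* That is 20% × (1 − p) for p = 0.2 to 0.4, and it applies only to a percentage contrast, which the plan does not specify. For the mean difference, day-0 doses add noise, and under the assumptions above not much.
- *Dose per 24 inpatient hours would solve the problem.* If dosing tapers, that rate rises when stay shortens, as the last check shows.
- *Day-0 practice or stay is known to have changed.* No passage shows this.

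Two further objections stand in part. A window starting at midnight on day 1 still includes doses given before the first session. However, it is a clock time that can be applied identically to controls, who have no session to anchor on. And any repair within the opioid outcome leaves the historical control in place.

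**Conclusion.** The concern holds. The opioid comparison is an unadjusted test of a total whose start is undefined, which on the plain reading includes doses before VR can act, and whose end varies with stay. With non-randomised controls from earlier years, a difference in day-0 dosing or length of stay can move it without any VR effect. That conclusion needs no assumed figures.

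The size does. Under the stated assumptions the shift is 7.5-10% for half a day of stay and 4-8% for a 20% difference in day-0 dose. With 35-50 against 350 patients, the half-day shift alone would give a positive test in roughly a third to a half of studies. The true figures are unknown, because the documents give no dosing or stay data.

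A reader might infer that any stay-driven difference is an artefact. That goes too far: VR may itself affect stay, and the total cannot separate the two. As this is a secondary outcome and the repair is modest, it is a change that should be made, not one on which the study depends.

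**What to change.** 1. Keep the whole-stay total as the declared opioid outcome. State the clock time or event at which it starts, and state that it mixes daily dosing with length of stay, which VR may itself affect.
2. Add a key fixed-window comparison in both arms: cumulative opioid dose from the start of postoperative day 1 through the end of postoperative day 2. Say in advance how patients discharged before the window closes are handled.
3. Report the dose from the end of surgery to the end of day 0 separately. Use it as a baseline covariate in the fixed-window comparison, which then needs a regression model with arm and day-0 dose in place of a two-sample test alone.
4. Treat a between-arm difference in day-0 dose as a negative-control signal. It precedes the first post-operative VR session, so it points to differences between eras (or in who enrolled) and calls for caution in reading the later comparison. The five-minute pre-operative device screening hardly weakens this check.
5. Do not make dose per 24 inpatient hours to discharge the main measure.

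**Cost.** The medication records used for the total must be split by administration time, in about 350 retrospective charts as well as the prospective ones. The plan does not say that timed doses are already being extracted, and it expects missing data in the retrospective arm, so some charts may be incomplete. Differences between eras in dosing after day 0 would remain and should be listed as a limitation.

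### No visible section names intra-operative analgesia as a variable to compare or adjust for, so a difference between the VR year and the control years could not be told apart from a VR effect

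*Combined protocol and SAP*

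**What the plan says.** **Opioid outcome.** Outcome Definitions, under Secondary Outcomes, states: "Opioid utilization will be assessed by calculating the total inpatient dose of opioids administered (as documented in the EMR) during the post-operative period". The matching secondary aim has the same window: "To determine if VR reduces the total amount of inpatient narcotic use in the acute post-operative period (until discharge) following spinal deformity surgery". The hypothesis beneath it is worded more widely ("reduced total inpatient narcotic administration during their hospital stay"), and Data Analysis says only that the tests "will be used to compare the total inpatient dose of opioids administered", with no time limit.

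**Data collected.** The surgical details run from the number "of spinal levels involved in fusion" through duration, blood loss and transfusion to complications. None is an anaesthetic or analgesic item. The same list includes "EPIC Medication History", without content or time window. Study Procedures, Retrospective Arm, lists "demographics, degree of scoliosis, surgical details, PT notes, pain medication regimens, associated pain scales, and relevant follow up notes", and the Prospective Arm text gives the same chart items. Appendix A is named as the data collection tool, but its content is not in the text available for review.

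**Design and analysis.** VR patients are recruited from 03/01/24 to 03/01/25. Controls come from about the preceding five years. VR starts on postoperative day 1. Data Analysis plans a between-group comparison of demographics and univariate tests for daily mean pain and total opioid dose. It contains no covariate, stratum, matching or calendar term. Study Limitations mentions missing variables and less accurate pain categorisation in the retrospective data, but not differences in analgesic practice over time.

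**The concern.** Analgesia given during surgery can affect pain and opioid need in the first post-operative days, when VR also begins. It is settled before any VR session, so it cannot be a result of VR. In a randomised trial it would balance on average. Here the arms are separated by calendar time, and nothing in the design or analysis provides that balance.

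A technique used more often in the VR year could lower both pain and post-operative opioid dose, and the two results would then look like independent support for VR. A technique used less often in that year would hide a real benefit. Use of Study Results says the data will inform a re-evaluation of the post-operative pain pathway, so a wrong attribution would have practical consequences.

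This determinant is worth naming separately from general drift in care because it precedes VR. Adjusting for it does not remove part of a VR effect, whereas adjusting for analgesia given after VR starts could.

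**Working it through.** **1. The plan's own figures.** There is no alpha, SD or power to reproduce, because Sample Size Justification describes a convenience sample. The accrual figures do reproduce:
- VR arm: (60 to 80) x (1 - 0.40) = 36 to 48, against the stated 35-50.
- Controls: 5 years x (60 to 80) = 300 to 400, midpoint 350, as stated.

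**2. Inputs for the illustration.**
- From the documents: about 350 controls, 35-50 VR patients (42 used here), and the hypothesised 1-point difference in pain.
- Assumed, because the documents give none: pain SD 2, two-sided alpha 0.05, the effect of the technique on mean pain, and its frequency in each arm.

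**3. Formulas.**
- SE = SD x sqrt(1/nVR + 1/nControl) = 2 x sqrt(1/42 + 1/350) = 0.327.
- Bias b = (difference in frequency of use) x (effect of technique).
- Rejection probability with no VR effect = Phi(b/SE - 1.96) + Phi(-b/SE - 1.96).

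**4. Results with no true VR effect.**

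| Use, controls v VR | Effect on mean pain | Bias | Rejection, formula | Rejection, simulation |
|---|---|---|---|---|
| equal | any | 0 | 5% | - |
| 30% v 50% | 0.5 point | 0.2 x 0.5 = 0.10 | 6.1% | 5.8% |
| 30% v 70% | 1 point | 0.4 x 1 = 0.40 | 23.2% | 22.2% |
| 20% v 80% | 1.5 points | 0.6 x 1.5 = 0.90 | 78.7% | 73.1% |

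The simulation used 4,000 runs and a residual SD of 2. It gives slightly lower rejection because the technique itself adds variance: in the third row the total SD is sqrt(4 + 0.3 x 0.7 x 1²) = 2.05 and the SE 0.335. For that row, moving the VR arm from 35 to 50 patients moves rejection by the formula from 20% to 26%.

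**5. Opposite direction.** Suppose VR truly lowers pain by 1 point and use is reversed (70% of controls, 30% of VR patients). The expected difference shrinks to 1 - 0.4 = 0.6. Power falls from Phi(1/0.327 - 1.96) = 86% to Phi(0.6/0.327 - 1.96) = 45%.

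**6. Dilution.** The table treats the effect as acting on mean pain over the stay. If a 1-point effect covered only half of the days averaged, the 30% v 70% bias would be 0.4 x 0.5 = 0.20 and rejection about 9%.

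**7. Adjustment.** With the technique as a single, perfectly recorded covariate, simulated rejection returns to 5.1% (30% v 70%) and 4.8% (20% v 80%). The SE rises from 0.335 to 0.339 and from 0.341 to 0.361 respectively. These are best-case figures: several covariates, misrecording or missing values would do less well.

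Nothing was computed for opioid dose, because the documents give no scale or spread for it.

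**The case against.** **The data may already be collected.** The entry "EPIC Medication History" is listed separately from the patient's own medication history, so it may well mean drugs given in hospital. Pain medication regimens are abstracted in both arms, and the Appendix A tool cannot be seen. This stands: it cannot be said that the data are absent. What can be said is that no visible section defines an intra-operative variable or gives it a use in the analysis.

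**Leaving intra-operative opioid out of the outcome is correct.** This also stands. Those doses precede VR and do not belong in its outcome. The wider hypothesis wording sits directly under an aim limited to the post-operative period, so this is a wording matter and not a second defect.

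**This is one instance of unadjusted historical control.** Largely true. Levels fused and duration are collected and not adjusted for either, so new fields without a change of analysis would achieve nothing. The point adds a specific pre-VR variable to that wider correction.

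**The size is assumed.** True. No section reports that technique varied or changed, and the illustrations run from zero bias to 0.9 point. A reader might infer that an operating-room effect will be reported as a VR benefit. The documents do not support that: they show neither a difference nor its direction. The Background remark that many practices are adopting multimodal strategies describes the field, not operating-room technique at this hospital.

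**Adjustment may fail.** If the centre changed technique for everyone at about the time VR began, technique and arm coincide and no model can separate them. This stands, and it limits what the fix can promise.

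**Conclusion.** The concern holds in a conditional form. With a historical control and univariate tests only, a difference between arms in intra-operative analgesia could not be distinguished from a VR effect on pain or post-operative opioid dose, in either direction. Whether there was such a difference is unknown.

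In the central illustration the bias is 0.4 point, which is 40% of the hypothesised 1-point difference, with false rejection of about 22-23% against a nominal 5%. This rests on the assumed SD of 2, the 30% v 70% frequencies and a 1-point effect lasting through the averaged days. Smaller or shorter-lived differences matter little, and balanced use gives no bias. The case for acting is that the variable is specific, precedes VR and may be obtainable from charts the study already plans to review.

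**What to change.** 1. **Collect.** Unless the Appendix A tool already does so, abstract from the existing chart in both arms total intra-operative opioid and whether neuraxial, regional or long-acting opioid analgesia was given.
2. **Describe.** Tabulate these by arm and by calendar year, with the number missing.
3. **Analyse.** Replace the univariate comparisons of pain and opioid dose with a regression that includes these variables alongside the surgical covariates already collected. Choose a small set of terms in advance, since only 35-50 VR patients are expected.
4. **State the limit.** If technique coincides almost entirely with arm, say that adjustment cannot separate it from VR and restrict the conclusion accordingly.
5. **Align the wording.** Bring the opioid hypothesis ("reduced total inpatient narcotic administration during their hospital stay") and the Data Analysis text into line with the post-operative outcome definition, so that every abstractor uses the same window.

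**Cost.** A few extra chart fields for about 350 controls and 35-50 VR patients, some missing retrospective values, a slightly larger standard error, and a short protocol change. No new patients or procedures are needed, and no change to patient care is proposed.
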